27 JUL 2023

BASED ON:

Protocol Version 7.0 (25 May 2022)

STUDY DRUG:

RTA 402, BARDOXOLONE METHYL

PROTOCOL NUMBER:

402-C-1808

STUDY TITLE:

A PHASE 3 TRIAL OF THE EFFICACY AND SAFETY OF BARDOXOLONE METHYL IN PATIENTS WITH AUTOSOMAL DOMINANT POLYCYSTIC KIDNEY DISEASE

SPONSOR:

Reata Pharmaceuticals, Inc.

[name]

[name]

[contact]

This study is being conducted in compliance with good clinical practice, including the archiving of essential documents.

The information contained herein is confidential and the proprietary property of Reata Pharmaceuticals, Inc. and any unauthorized use or disclosure of such information without the prior written authorization of Reata Pharmaceuticals, Inc. is expressly prohibited.

SIGNATURE PAGE

This document has been prepared by:

[REDACTED], M.S.

*{See Appended Electronic Signature
Page}*

Signature

Date

Reata Pharmaceuticals, Inc.

This document has been reviewed and accepted by:

[REDACTED] M.S.

*{See Appended Electronic Signature
Page}*

Signature

Date

Reata Pharmaceuticals, Inc.

[REDACTED] M.D.

*{See Appended Electronic Signature
Page}*

Signature

Date

Reata Pharmaceuticals, Inc.

[REDACTED] PharmD

*{See Appended Electronic Signature
Page}*

Signature

Date

Reata Pharmaceuticals, Inc.

TECHNICAL SUMMARY REPORT (TSR)

Name of Sponsor/Company Reata Pharmaceuticals	Individual Study Table Referring to Part of the Dossier: Volume:	(For National Authority Use Only):
Name of Finished Product: Bardoxolone methyl	Page:	
Name of Active Ingredient: Bardoxolone methyl		
Title of Study: A Phase 3 Trial of the Efficacy and Safety of Bardoxolone Methyl in Patients with Autosomal Dominant Polycystic Kidney Disease		
Studied period: ~6 years (Estimated based on enrollment of the first patient [May 2019] and the estimated date of last patient last visit [November 2025])	Phase of development: 3	

Study Endpoints:

Primary Efficacy Endpoint

- Off-treatment change from baseline in estimated glomerular filtration rate (eGFR) at Week 108.

Secondary Efficacy Endpoint

- Change from baseline in eGFR at Week 100.

[Redacted]

- [Redacted]
- The off-treatment change from baseline in eGFR at Week 112.
- [Redacted]
- [Redacted]
- [Redacted]
- [Redacted]
- [Redacted]
- [Redacted]
- [Redacted]
- [Redacted]
- [Redacted]
- [Redacted]
- [Redacted]
- [Redacted]
- [Redacted]
- [Redacted]
- [Redacted]
- [Redacted]
- [Redacted]

- [REDACTED]
- [REDACTED]
- [REDACTED]
- [REDACTED]
- [REDACTED]
- [REDACTED]
- [REDACTED]
- [REDACTED]
- [REDACTED]
- [REDACTED]

Safety Endpoints

- Frequency, intensity, and relationship to study drug of adverse events (AEs) and serious adverse events (SAEs) and change from baseline in the following assessments: vital sign measurements, 12-lead electrocardiograms (ECGs), clinical laboratory measurements, pediatric growth (height and weight), and sexual maturity using Tanner staging.

Methodology:

This international, multi-center randomized, double-blind, placebo-controlled Phase 3 trial will study the safety, tolerability, and efficacy of bardoxolone methyl in qualified patients with ADPKD. Approximately 850 patients will be enrolled.

Patients will be randomized 1:1 to either bardoxolone methyl or placebo. Randomization will be stratified by eligibility eGFR category (30 to <60; ≥60 to 90), concomitant tolvaptan use (yes, no), and screening albumin to creatinine ratio (ACR; ≤300 mg/g, >300 mg/g). Patients randomized to placebo will remain on placebo throughout the study, undergoing sham titration. Patients with eGFR 60 to 90 mL/min/1.73 m² at screening should not comprise more than approximately 40% of enrolled patients.

The maximum bardoxolone methyl dose will be determined by baseline proteinuria status. Patients with baseline ACR ≤300 mg/g will be titrated to a maximum dose of 20 mg, and patients with baseline ACR >300 mg/g will be titrated to a maximum dose of 30 mg. Patients receiving bardoxolone methyl will start with once-daily dosing at 5 mg and will dose-escalate to 10 mg at Week 2, to 20 mg at Week 4, and then to 30 mg at Week 6 (only if baseline ACR >300 mg/g) unless contraindicated clinically and approved by the medical monitor. Dose de-escalation is permitted during the study if indicated clinically, and subsequent dose re-escalation is also permitted to meet the dosing objective of the highest tolerated dose.

All patients in the study will follow the same visit and assessment schedule. Following randomization on Day 1, patients will be assessed during treatment in person at Week 1, 2, 4, 6, 8, 12, 24, 36, 48, 52, 64, 76, 88, and 100 and by telephone contact on Day 3, 10, 21, 31, 38, and 45. Patients will continue study drug treatment through Week 100. Patients will also be scheduled to be assessed at an in-person follow-up visit at Weeks 103, 104, 108, and 112 after the end of treatment, respectively.

Efficacy endpoints will be analyzed after final database lock.

The conduct of the study, according to protocol specifications, was impacted by the COVID-19 (Coronavirus Disease 2019) pandemic. As a result, and as of Version 4 of the protocol, modifications intended to address access to and administration of study drug, and adherence to protocol-specified visits and laboratory assessments were implemented. These modifications are described in Appendix 1 of the protocol (COVID-19 Mitigations), Appendix 2 of the protocol (Use of Home Healthcare), and throughout the protocol.

Number of Subjects (planned and analyzed):

Planned: Approximately 850

Diagnosis and main criteria for inclusion:

1. Male and female patients $12 \leq \text{age} \leq 70$ upon study consent;
2. Diagnosis of ADPKD:
 - a. For adult ($18 \leq \text{age} \leq 70$) diagnosis of ADPKD by modified Pei-Ravine criteria:
 - i. at least 3 cysts per kidney by sonography or at least 5 cysts by CT or MRI with family history of ADPKD; or
 - ii. at least 10 cysts per kidney by any radiologic method and exclusion of other cystic kidney diseases if without family history;
 - b. For adolescent ($12 \leq \text{age} < 18$) diagnosis of ADPKD by:
 - i. the presence of family history and/or genetic diagnosis and the presence of at least 1 cyst of 0.5 cm on ultrasound or MRI; or
 - ii. patients without a family history or genetic diagnosis must have at least 10 bilateral renal cysts in total, and exclusion of other cystic kidney diseases.
3. eGFR must:
 - a. Have a percent difference $\leq 25\%$ at screening (the values at Screen A and Screen B) and;
 - b. Have an average (the values at Screen A and Screen B) ≥ 30 to ≤ 90 mL/min/1.73 m² for patients 12 to 55 years or ≥ 30 to ≤ 44 mL/min/1.73 m² for patients 56 to 70 years and;
 - c. Support ADPKD disease progression (i.e., average yearly eGFR decline of ≥ 2.0 mL/min/1.73 m² for the past 2 years) for patients with either screening eGFR ≥ 60 to ≤ 90 mL/min/1.73 m² or age 56 to 70 years;
4. ACR ≤ 2500 mg/g at Screen B visit;
5. Systolic blood pressure ≤ 140 mmHg and diastolic blood pressure ≤ 90 mmHg at Screen A or Screen B visit after a period of rest. Patients receiving an angiotensin-converting enzyme (ACE) inhibitor and/or an angiotensin II receptor blocker (ARB) must be on a stable dose for at least 6 weeks prior to the Screen A visit;
6. Adequate bone marrow reserve and organ function at the Screen A visit as follows:
 - a. Hematologic: Absolute neutrophil count $> 1.5 \times 10^9$ /L, platelets $> 100 \times 10^9$ /L, hemoglobin (Hgb) ≥ 9 g/dL;
 - b. Hepatic: Total bilirubin (TBL), alanine aminotransferase (ALT), and aspartate aminotransferase (AST) \leq the upper limit of normal (ULN);
7. Able to swallow capsules;
8. Willing and able to comply with scheduled visits, treatment plan, laboratory tests, and other study procedures;
9. Evidence of a personally signed and dated informed consent/assent document indicating that the patient has been informed of all pertinent aspects of the study prior to initiation of any protocol-mandated procedures.
10. Patients receiving an sodium glucose co-transporter 2 inhibitor must be on a stable dose for at least 4 weeks prior to the Screen A visit

Major exclusion criteria:

1. Prior exposure to bardoxolone methyl;
2. Use of tolvaptan within 2 months prior to Screen A. Initiation of concomitant tolvaptan use during the study is not permitted;
3. History of administration of polycystic kidney disease-modifying agents (somatostatin analogues) within 2 months prior to the Screen A visit;
4. B-type natriuretic peptide (BNP) level > 200 pg/mL at Screen A visit;

5. Uncontrolled diabetes (HbA1c >11.0%) at Screen A visit;
6. Serum albumin <3 g/dL at Screen A visit;
7. History of intracranial aneurysms;
8. Kidney or any other solid organ transplant recipient or a planned transplant during the study;
9. Acute dialysis or acute kidney injury within 12 weeks prior to Screen A visit or during Screening;
10. History of clinically significant left-sided heart disease and/or clinically significant cardiac disease, including but not limited to any of the following:
 - a. Clinically significant congenital or acquired valvular disease;
 - b. Left ventricular ejection fraction <40% (based on echocardiogram performed at Screen A visit or within 6 months prior to Day 1);
 - c. Pericardial constriction (based on echocardiogram performed at Screen A visit or within 6 months prior to Day 1);
 - d. Restrictive or congestive cardiomyopathy (based on echocardiogram performed at Screen A visit or within 6 months prior to Day 1);
 - e. Symptomatic coronary disease (prior myocardial infarction, percutaneous coronary intervention, coronary artery bypass graft surgery, or angina);
 - f. History of hospitalization for heart failure;
 - g. Cardiac insufficiency, defined as New York Heart Association Class III or IV;
 - h. History of untreated atrial fibrillation;
 - i. History of unstable arrhythmias;
11. Systolic BP <90 mm Hg at Screen A visit after a period of rest;
12. BMI <18.5 kg/m² at the Screen A visit;
13. History of malignancy within 5 years prior to Screen A visit, with the exception of localized skin or cervical carcinomas;
14. Systemic immunosuppression for more than 2 weeks, cumulatively, within the 12 weeks prior to randomization or anticipated need for immunosuppression during the study;
15. Untreated or uncontrolled active bacterial, fungal, or viral infection;
16. Participation in other interventional clinical studies within 30 days prior to Day 1;
17. Unwilling to practice acceptable methods of birth control (both males who have partners of child-bearing potential and females of childbearing potential) during Screening, while taking study drug, and for at least 30 days after the last dose of study drug is ingested;
18. Women who are pregnant or breastfeeding;
19. Known hypersensitivity to any component of the study drug;
20. Any abnormal laboratory level that, in the opinion of the investigator, would put the patient at risk by trial enrollment;
21. Patient is, in the opinion of the investigator, unable to comply with the requirements of the study protocol or is unsuitable for the study for any reason;
22. Coronavirus disease 2019 (COVID-19) pneumonia, related acute kidney injury, or related hospitalization within 6 months prior to Day 1.

Test product, dose and mode of administration:

Bardoxolone methyl will be administered orally at 5, 10, 20, or 30 mg once daily (QD).

Duration of treatment:

Bardoxolone methyl or placebo will be administered through Week 100.

Reference therapy, dose and mode of administration:

Placebo will be administered orally through Week 100, QD.

Criteria for evaluation (see protocol section 6.2, 11.0):

Efficacy: Change from baseline in eGFR; [REDACTED]

Safety: Results of laboratory results (clinical chemistry, hematology, urinalysis, and microscopy), vital sign measurements, ECG results, pediatric growth (height and weight), [REDACTED], AEs, and SAEs.

Statistical methods:

With 850 patients enrolled, the study will have approximately 80% power to detect a difference between the 2 treatment groups in change from baseline eGFR of 2.3 mL/min/1.73 m². The power calculation was based on a 2-sample t-test as an estimate for the planned analysis of covariance (ANCOVA) analysis and assumes the following:

- Overall two-sided Type I error rate total of 0.05;

1. LIST OF ABBREVIATIONS

The following abbreviations and special terms are used in this statistical analysis plan (SAP).

Table 1. LIST OF ABBREVIATIONS

Abbreviation	Term
ABPM	ambulatory blood pressure monitoring
ACEi	angiotensin converting enzyme inhibitor
ACR	albumin/creatinine ratio
ACR_STRAT	ACR strata used in randomization
ADPKD	autosomal dominant polycystic kidney disease
██████████	██
AE	adverse event
ALT	alanine aminotransferase
ALP	alkaline phosphatase
ANCOVA	analysis of covariance
ARB	angiotensin II receptor blocker
AST	aspartate aminotransferase
BARD	bardoxolone methyl
BMI	body mass index
BNP	B-type natriuretic peptide
██████	██
CKD	chronic kidney disease
CKD-EPI	Chronic Kidney Disease Epidemiology Collaboration
CSR	clinical study report
CT	computed tomography
ECG	electrocardiogram
eCRF	electronic case report form
eGFR	estimated glomerular filtration rate
eGFR_STRAT	eGFR strata used in randomization
ESKD	end stage kidney disease
FDA	Food and Drug Administration (US)
FMV	first morning void
ICH	International Council for Harmonisation of Technical Requirements for Pharmaceuticals for Human Use

Abbreviation	Term
INR	international normalized ratio
ITT	intent-to-treat
IWRS	Interactive Web Response System
KDIGO	Kidney Disease: Improving Global Outcomes
LLD	lower limit of detection
MedDRA	Medical Dictionary for Regulatory Activities
MMRM	mixed model repeated measures
MRI	magnetic resonance imaging
NCS	Not clinically significant
NT-ProBNP	N-Terminal Pro-Brain Natriuretic Peptide
OTAE	off-treatment adverse event
████	████████████████████
pH	potential of hydrogen
PK	pharmacokinetic(s)
PT	preferred term
QTcF	corrected QT interval using Fridericia's formula
SAE	serious adverse event
SAP	statistical analysis plan
SCr	serum creatinine
SD	standard deviation
SOC	system organ class
STD	Study Termination Date
TBL	total bilirubin
TEAE	treatment-emergent adverse event
TLFs	tables, listings, and figures
ULD	upper limit of detection
ULN	upper limit of normal
US	United States
WOCBP	women of childbearing potential

2. INTRODUCTION

This statistical analysis plan (SAP) describes the planned analyses and data displays to be included in the Clinical Study Report (CSR) for Study 402-C-1808. This SAP was developed in accordance with International Council for Harmonisation of Technical Requirements for Pharmaceuticals for Human Use (ICH) E9 guidelines. All decisions regarding the final analysis, as defined in this SAP document, were made prior to Database Lock (unblinding) of the study data.

The SAP is based on:

- Protocol 402-C-1808, Version 7.0, dated 25 May 2022
- ICH guidelines E4 (Dose-Response Information to Support Drug Registration) and E9 (Statistical Principles for Clinical Trials)
- Feedback received from FDA throughout clinical development, including the following communications:
 - FDA End of Phase 2 Meeting Minutes [REDACTED] for the 31 October 2018 meeting
 - FDA Advice/Information Request [REDACTED] dated 16 July 2019
 - FDA Advice/Information Request [REDACTED] dated 08 October 2020
 - FDA Type B Meeting Minutes [REDACTED] for the 23 July 2021 meeting
 - FDA Type A Meeting Minutes [REDACTED] for the 08 April 2022 meeting

This SAP describes the study populations, how variables are derived, how missing data are handled, and details concerning the statistical methods to be used to analyze the safety and efficacy data from Study 402-C-1808. Should the SAP and the protocol be inconsistent with respect to the planned analyses, the language of the SAP is governing.

This version of the SAP describes the analyses as planned prior to the final database lock. This SAP will be finalized, approved by the Reata Pharmaceuticals, and placed on file before the database lock. Unless otherwise specified, the final CSR will summarize these analyses. Any deviations from the final approved SAP will be documented in the CSR. Any analyses in addition to those specified in the SAP prior to the database lock are considered ad hoc and will be documented in the CSR.

In May 2023, Kyowa Kirin Co., Ltd. (Kyowa Kirin) announced results from AYAME (402-006), a Phase 3, multi-center, randomized, double-blind, placebo-controlled trial to evaluate the efficacy and safety of bardoxolone methyl (bardoxolone) for patients with diabetic kidney disease. The study enrolled 1013 patients who were treated with 5 to 15 mg of bardoxolone or placebo for 3 to 4 years.

The AYAME (402-006) study met the primary endpoint and key secondary endpoint; however, there was no separation in the occurrence of end-stage renal disease events between the 2 groups. Based on the AYAME (402-006) efficacy results, Kyowa Kirin and Reata have decided to discontinue clinical development of bardoxolone.

This decision was communicated to all sites on 10 May 2023, which is referred to as the study drug termination (SDT) date.

3. STUDY OBJECTIVES AND ENDPOINTS

3.1. Study Objectives

3.1.1. Primary Objectives

- To assess the off-treatment change from baseline in estimated glomerular filtration rate (eGFR) at Week 108.
- To assess safety and tolerability.

3.1.2. Secondary Objective

- To assess the change from baseline in eGFR at Week 100.

- [Redacted]
- [Redacted]
- To assess the off-treatment change from baseline in eGFR at Week 112.
- [Redacted]
[Redacted]
- [Redacted]
[Redacted]
- [Redacted]
[Redacted]
- [Redacted]
[Redacted]
- [Redacted]
[Redacted]
[Redacted]
- [Redacted]
[Redacted]
- [Redacted]
- [Redacted]
- [Redacted]
[Redacted]
- [Redacted]
- [Redacted]
[Redacted]
- [Redacted]

- [REDACTED]
- [REDACTED]
- [REDACTED]
- [REDACTED]
- [REDACTED]
- [REDACTED]
- [REDACTED]
- [REDACTED]
- [REDACTED]
- [REDACTED]
- [REDACTED]
- [REDACTED]
- [REDACTED]
- [REDACTED]
- [REDACTED]

3.2. Study Endpoints

In patients with autosomal dominant polycystic kidney disease (ADPKD), the study will compare those receiving bardoxolone methyl to those receiving placebo with respect to several endpoints. The timing for analyzing study endpoints is described in Section 5. Primary efficacy analyses are described in Section 8 [REDACTED]

3.2.1. Primary Efficacy Endpoint

- Off-treatment change from baseline in eGFR at Week 108.

3.2.2. Secondary Efficacy Endpoint

- Change from baseline in eGFR at Week 100.

- [REDACTED]
- [REDACTED]
- The off-treatment change from baseline in eGFR at Week 112.
- [REDACTED]
- [REDACTED]
- [REDACTED]
- [REDACTED]
- [REDACTED]

- [REDACTED]
[REDACTED]
- [REDACTED]
[REDACTED]
- [REDACTED]
[REDACTED]
- [REDACTED]
[REDACTED]
- [REDACTED]
- [REDACTED]
- [REDACTED]
- [REDACTED]
- [REDACTED]
[REDACTED]
- [REDACTED]
- [REDACTED]
- [REDACTED]
- [REDACTED]
- [REDACTED]
[REDACTED]
- [REDACTED]
- [REDACTED]
- [REDACTED]
- [REDACTED]
- [REDACTED]
[REDACTED]
- [REDACTED]
- [REDACTED]
- [REDACTED]
- [REDACTED]

3.2.4. Safety Endpoints

- Frequency, intensity, and relationship to study drug of adverse events (AEs) and serious adverse events (SAEs) and change from baseline in the following assessments: vital sign measurements, 12-lead electrocardiograms (ECGs), clinical laboratory measurements, pediatric growth (height and weight), and sexual maturity using Tanner staging.

4. STUDY DESIGN

4.1. Summary of Study Design

This international, multi-center, randomized, double-blind, placebo-controlled Phase 3 trial will study the safety, tolerability, and efficacy of bardoxolone methyl in qualified patients with ADPKD. Approximately 850 patients will be enrolled.

Patients will be randomized 1:1 to either bardoxolone methyl or placebo. Randomization will be stratified by eligibility eGFR category (30 to <60; ≥ 60 to 90), concomitant tolvaptan use (yes, no), and screening albumin to creatinine ratio (ACR; ≤ 300 mg/g, >300 mg/g). Patients randomized to placebo will remain on placebo throughout the study, undergoing sham titration. Patients with eGFR 60 to 90 mL/min/1.73 m² at screening should not comprise more than approximately 40% of enrolled patients.

The maximum bardoxolone methyl dose will be determined by baseline proteinuria status. Patients with baseline ACR ≤ 300 mg/g will be titrated to a maximum dose of 20 mg, and patients with baseline ACR >300 mg/g will be titrated to a maximum dose of 30 mg. Patients receiving bardoxolone methyl will start with once-daily dosing at 5 mg and will dose-escalate to 10 mg at Week 2, to 20 mg at Week 4, and then to 30 mg at Week 6 (only if baseline ACR >300 mg/g) unless contraindicated clinically and approved by the medical monitor. Dose de-escalation is permitted during the study if indicated clinically, and subsequent dose re-escalation is also permitted to meet the dosing objective of the highest tolerated dose.

[figure not shown]
All patients in the study will follow the same visit and assessment schedule. Following randomization on Day 1, patients will be scheduled to be assessed during treatment at Week 1, 2, 4, 6, 8, 12, 24, 36, 48, 52, 64, 76, 88, and 100 and by telephone contact on Day 3, 10, 21, 31, 38, and 45. Patients will continue study drug treatment through Week 100. Patients will also be scheduled to be assessed at an in-person follow-up visit at Weeks 103, 104, 108, and 112, after the end of treatment, respectively. The Data Monitoring Committee performs quarterly reviews of unblinded data for safety throughout the study.

Efficacy endpoints will be analyzed after all enrolled patients have completed the study and the final database lock.

The conduct of the study, according to protocol specifications, was impacted by the COVID-19 (Coronavirus Disease 2019) pandemic. As a result, modifications intended to address access to and administration of investigational product (IP), and adherence to protocol-specified visits and laboratory assessments were implemented and are described in [Appendix 1 of the protocol](#) (COVID-19 Mitigations), [Appendix 2 of the protocol](#) (Use of Home Healthcare), and throughout the protocol. The COVID-19-related impact on study conduct will be summarized as described in Section 10 of this SAP.

Figure 1. STUDY SCHEMA

Schema for Study of Bardoxolone Methyl in Patients with ADPKD

4.2. Definition of Study Drugs

Bardoxolone methyl capsules, 5 mg (size #4), 10 mg (size #2), 15 mg (size #1), and 20 mg (size #0) may be used in this study. The 30 mg dose will be given as two 15 mg capsules. Placebo capsules will have matching capsule sizes to have the same appearance as the active doses.

4.3. Sample Size Considerations

4.3.1. Primary Endpoints

With 850 patients enrolled, the study will have approximately 80% power to detect a difference between the 2 treatment groups in change from baseline eGFR of 2.3 mL/min/1.73 m². The power calculation was based on a 2-sample t-test as an estimate for the planned analysis of covariance (ANCOVA) analysis and assumes the following:

- Overall two-sided Type I error rate total of 0.05;
- Standard deviation of change from baseline in eGFR of 12 mL/min/1.73 m²;
- Analyses are based on the intent-to-treat (ITT) population;
- Missing data will be imputed using multiple imputation.

PASS 13 software was used to calculate sample size.

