6. GENERAL CONSIDERATIONS FOR DATA ANALYSES AND HANDLING

The efficacy and safety analyses use the analysis sets defined in Section 6.3. Patient listings (as appropriate) of all analysis data that support summary tables and/or figures are provided along with their source data. The summary tables do not include measurements from patients excluded from the pre-defined analysis sets or extra measurements (such as unscheduled or repeat assessments) not closest to the target study day unless specified otherwise, but the patient listings do include these data. Missing data are not imputed, unless otherwise specified. In general, patient listings are sorted by treatment group, patient number and assessment date (time and parameter, as applicable).

Any laboratory value (including eGFR), vital sign assessment, or ECG value collected after ESKD is considered invalid and will be treated as missing.

Efficacy and safety data collected while a patient has temporarily discontinued study drug will be included in analyses. All data will be presented in by-patient listings.

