6.6. Handling of Missing Data

6.6.1. Missing Efficacy Endpoint Data

Missing data will not be imputed for analyses of efficacy endpoints.

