8.3. Multiple Comparisons and Multiplicity

All objectives are presented with nominal significance levels for descriptive purposes only.

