8.4. Primary Endpoint

8.4.1. Primary Endpoint Analysis

The primary endpoint of this study is the off-treatment change from baseline in eGFR at Week 108. The ITT population will be used for all analyses. For all patients enrolled in the trial, Week 108 is the off-treatment eGFR assessed closest to 108 weeks after Study Day 1. For a patient who completed 2 years of treatment, the 8-week drug treatment withdrawal period occurs at Week 108 (i.e., 56 days after last dose). For a patient who stopped drug treatment early, the eGFR assessment at Week 108 is analyzed, irrespective of how long a patient has been off-treatment. Analysis of Week 108 (after a planned 8-week drug treatment withdrawal period) assesses the preserved drug benefit (relative to placebo) following withdrawal of treatment.

The off-treatment change from baseline eGFR at Week 108 for patients treated with bardoxolone methyl is compared to placebo using an ANCOVA model, with BASE_eGFR as a covariate, and TRT as fixed effects. The ANCOVA analysis uses eGFR values collected in the Week 108 analysis window (Section 6.5.2), which includes the follow-up assessment at Week 108 for patients who discontinued treatment early irrespective of time after last dose.

Missing Week 108 eGFR data will not be imputed.

The difference between bardoxolone methyl and placebo in change from baseline of eGFR is estimated along with the 95% confidence interval at Week 108.

Example SAS code as follows:

```
proc glm data=efficacy;
  class TRT ACR_STRAT;
  model DELT_eGFR=trt ACR_strat base_egfr /solution;
  lsmeans trt / diff stderr pdiff cl alpha=0.05;
run;
```

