The difference between bardoxolone methyl and placebo in change from baseline in eGFR is estimated along with the 95% confidence interval at Week 100 for the primary analysis of the secondary endpoint.

Missing eGFR data will not be imputed.

SAS example as follows:

```
proc mixed data=OUT2 method=reml alpha=0.05 covtest;  
  class VISITNUM(ref=LAST)  
        TRT(ref=FIRST) SUBJID ACR_STRAT;
```

```
model DELT_eGFR = BASE_eGFR ACR_STRAT TRT VISITNUM  
          TRT*VISITNUM BASE_eGFR*VISITNUM / solution ddfm=kr;  
repeated VISITNUM / subject=SUBJID type=un r;  
lsmeans TRT*VISITNUM / pdiff om cl e;  
estimate 'Estimate at Week 100' TRT 1 -1 TRT*VISITNUM 1 -1 / cl;  
ods output LSMeans=LSM diffs=Diff;
```

run;

[figure not shown]
A plot of least squared means from the MMRM model at each visit by treatment arm will be created.

[figure not shown]

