8.6.1.2. Off Treatment eGFR ANCOVA Analyses – No Imputation for Missing Data

The ANCOVA analysis (defined in Section 8.4.1) will be performed by using eGFR values collected at [redacted] Week 112 off-treatment analysis visits (Table 4). Missing eGFR data per visit are not imputed.

The difference between bardoxolone methyl and placebo in change from baseline of eGFR is estimated along with the 95% confidence interval at each off-treatment visits.

[figure not shown]

[REDACTED]

[REDACTED]

[REDACTED]

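### The SAP's 80% power statement assumes multiple imputation that its own analysis sections rule out, and it allows nothing for missing Week 108 eGFR

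*SAP*

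**What the plan says.** SAP Section 4.3.1 states: "With 850 patients enrolled, the study will have approximately 80% power to detect a difference between the 2 treatment groups" of 2.3 mL/min/1.73 m² in change from baseline eGFR. The calculation is a two-sample t-test standing in for the planned ANCOVA. It assumes a two-sided error rate of 0.05, an SD of 12, the intent-to-treat population, and "Missing data will be imputed using multiple imputation". The statistical methods part of the TSR carries the same bullet, as does protocol Section 12.1.

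The parts of the SAP that direct the analysis give the reverse rule:

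- Section 6, general default: "Missing data are not imputed, unless otherwise specified".
- Section 6.6.1, all efficacy endpoints: "Missing data will not be imputed for analyses of efficacy endpoints".
- Section 8.4.1, primary endpoint: "Missing Week 108 eGFR data will not be imputed".
- Section 8.5.1, secondary endpoint: "Missing eGFR data will not be imputed".
- Section 8.6.1.2, off-treatment analyses including Week 112: "Missing eGFR data per visit are not imputed".

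On inference, Section 8.3 says: "All objectives are presented with nominal significance levels for descriptive purposes only". Section 2 records that development was discontinued and that sites were told on 10 May 2023. Protocol Section 12.3.1 commits to sensitivity analyses for missing data, including a tipping-point analysis.

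**The concern.** Both statements stand in the SAP, so the rule that the SAP prevails over the protocol does not settle the conflict. Section 4.3.1 is written in the future tense and is not marked as a historical planning note, although the SAP is dated 27 July 2023, after the stop.

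The second difficulty is that the power figure contains no allowance for missing Week 108 values, and complete data cannot be taken for granted. Week 108 falls a little over two years after first dose, and the TSR had expected the last patient's last visit in November 2025. Later-enrolled patients could therefore not have reached Week 108 by 10 May 2023. Section 6 also treats eGFR collected after end stage kidney disease as missing.

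The Week 108 difference and its 95% confidence interval remain the main efficacy result. A reader relying on Section 4.3.1 would expect the precision of 850 patients, supported by imputation. The planned analysis offers no imputation, and 850 observed values only if nothing is missing.

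**Working it through.** **Inputs (SAP Sections 4.3.1 and 4.4).** Difference δ = 2.3; SD σ = 12; two-sided α = 0.05; 1:1 allocation; N = 850.

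**Formulas.** With N evaluable patients split equally, the standard error of the difference is σ√(4/N) = 24/√N. Power comes from the noncentral t distribution with N − 2 degrees of freedom and noncentrality δ√N/24. The 95% confidence interval half-width is t(0.975, N − 2) × 24/√N, with t about 1.963 throughout.

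**Reproducing the stated figure.** For N = 850, √N = 29.15 and the noncentrality is 2.3 × 29.15/24 = 2.79. Power is 79.7% (79.8% by the normal approximation), which matches the stated figure. By the exact t-test, 80% needs 429 per arm, or 858 in total. The match uses all 850 patients, so nothing is held back for missing values.

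**Observed values only.** The current documents give no missing rate, so 10% and 15% are assumptions. The 15% is borrowed from superseded protocol text as a reference value only.

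| Assumed missing | Evaluable N | Noncentrality | Power | 95% CI half-width |
|---|---|---|---|---|
| 0% | 850 | 2.79 | 79.7% | 1.62 |
| 10% | 765 | 2.65 | 75.4% | 1.70 |
| 15% | 722.5 | 2.58 | 73.0% | 1.75 |

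For example, at 15%: 1.963 × 24/√722.5 = 1.963 × 24/26.88 = 1.75.

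**What the table leaves out.** It describes the t-test named in Section 4.3.1. The ANCOVA adjusts for baseline eGFR, which multiplies the residual variance by 1 − r², where r is the correlation between baseline and change. To cancel a 15% loss exactly, 1 − r² must equal 0.85, so r is about 0.39. The documents give no r, and protocol Section 12.1 expects the ANCOVA to have roughly the t-test's power. The table also covers loss of precision only. It says nothing about bias.

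**The case against.** **The paragraph is only planning history.** Section 4.3.1 largely repeats protocol Section 12.1 and explains how 850 was chosen. The operative rules are consistent, so no analyst would be led to run the wrong model. The sample size cannot change and no powered test remains. This largely stands and is why the point is minor. It does not make the statement correct: the SAP still presents a current power claim on an assumption that it rejects elsewhere.

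**The actual precision will be reported anyway.** This is true. Section 8.4.1 gives the interval, Sections 6.2 and 8.1 give counts by arm, and Section 7.1 already tabulates follow-up through Week 108, so no further table is required. The power paragraph still needs correcting.

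**The lower effect size already allows for dropout.** The amendment log attributes the reduction from 3.1 to 2.3 to dilution by patients who stop drug early but are still measured. That is not an allowance for values never observed.

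**Stronger readings that the documents do not support.**

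- A reader might infer that the sponsor dropped the tipping-point analysis. None is visible in the readable SAP, but much of Section 8.6 is redacted, so an omission cannot be claimed.
- A reader might turn the dates into a missing rate or an exact range of first-dose dates. Enrolment by date is not given. For completers, Week 108 runs from the last dose, and the Week 100 visit may fall up to five days early. Version 6.0, which added the Week 108 visits, took effect only after the required approvals. Neither end of such a range can be fixed.
- A reader might suppose that restoring imputation would make 80% correct. Imputation recovers only part of the lost information, depending on predictors for which the documents give no correlations.

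**Conclusion.** The internal contradiction is established. The roughly 80% power in Section 4.3.1 and the TSR belongs to the stated t-test with a Week 108 eGFR from every one of the 850 patients. It is attached to an imputation method that the SAP does not use. The arithmetic behind 80% is sound; the missing-data assumption printed beside it is not the one planned.

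At an assumed 10% to 15% missing, the loss is about 4 to 7 percentage points of power (79.7% to 75.4% or 73.0%), and the half-width grows by 0.08 to 0.13 mL/min/1.73 m². This rests on an SD of 12, equal missing proportions in the two arms and no gain from baseline adjustment. The true missing rate is unknown, and the documents give neither size nor direction for any bias.

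Severity is minor: development has ended and all testing is nominal. The tipping-point analysis is a question for the sponsor, not a finding.

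**What to change.** 1. In SAP Section 4.3.1 and the TSR, replace the multiple-imputation bullet with the no-imputation rule of Sections 6.6.1 and 8.4.1.
2. In both places, label 80% as the original design figure, which requires a Week 108 eGFR from all 850 patients, and note that testing is descriptive under Section 8.3.
3. Report the 95% confidence interval half-width for the number of patients with an evaluable Week 108 eGFR.
4. As a query only: confirm whether the tipping-point analysis of protocol Section 12.3.1 is kept, possibly in redacted text, or record why it was dropped.

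The cost is a wording change in two places and one derived figure. The primary analysis is unchanged, and no new data or patients are needed. Programming arises only if a tipping-point analysis is kept and not yet written. The precision stated will look less favourable if Week 108 values are missing.
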